APPENDIX 3 WOMEN OF CHILDBEARING POTENTIAL DEFINITIONS AND METHODS OF CONTRACEPTION

Definitions

Woman of Childbearing Potential

A woman is considered fertile following menarche and until becoming postmenopausal unless permanently sterile. Permanent sterilization methods include hysterectomy, bilateral salpingectomy, and bilateral oophorectomy.

Women in the following categories are not considered WOCBP:

- Premenarchal
 - Premenopausal female with 1 of the following:
 - Documented hysterectomy
 - o Documented bilateral salpingectomy
 - Documented bilateral oophorectomy

Note: Documentation can come from the site personnel's review of the participant's medical records, medical examination, or medical history interview.

- Postmenopausal female
 - A postmenopausal state is defined as 12 months of amenorrhea in a woman over age 45 years in the absence of other biological or physiological causes. In addition, females must have a serum FSH level > 40 mIU/mL to confirm menopause.

Note: Females treated with hormone replacement therapy (HRT) are likely to have artificially suppressed FSH levels and may require a washout period in order to obtain a physiologic FSH level. The duration of the washout period is a function of the type of HRT used. The duration of the washout periods below are suggested guidelines and the investigators should use their judgement in checking serum FSH levels.

- 1 week minimum for vaginal hormonal products (rings, creams, gels)
- 4 week minimum for transdermal products
- 8 week minimum for oral products

Other parenteral products may require washout periods as long as 6 months. If the serum FSH level is > 40 mIU/mL at any time during the washout period, the woman can be considered postmenopausal.

Contraception Guidance for Female Participants of Child Bearing Potential

One of the contraception methods listed below as "**Highly Effective**" is required to be used during this study and until the end of relevant systemic exposure, defined as 5 days after the end of study treatment, plus 30 days. Hormonal contraception and methods listed as not highly effective or ineffective below are not permitted.

Contraceptive Methods Classified as Highly Effective

User Independent Methods

- Intrauterine device (IUD)^c
- Bilateral tubal occlusion
- Vasectomized partner

A vasectomized partner is a highly effective contraception method provided that the partner is the sole male sexual partner of the WOCBP and the absence of sperm has been confirmed. If not, an additional highly effective method of contraception should be used.

Sexual abstinence

Sexual abstinence is considered a highly effective method only if defined as refraining from heterosexual intercourse during the entire period of risk associated with the study treatment. The reliability of sexual abstinence needs to be evaluated in relation to the duration of the study and the preferred and usual lifestyle of the participant.

- It is not necessary to use any other method of contraception when complete abstinence is elected.
- WOCBP participants who choose complete abstinence must continue to have pregnancy tests.
- Acceptable alternate methods of highly effective contraception must be discussed in the event that the WOCBP participants chooses to forgo complete abstinence

Contraceptive Methods Not Classified as Highly Effective

User Dependent Methods

Failure rate of > 1% per year when used consistently and correctly.

[figure not shown]
- Male or female condom with or without spermicide. Male and female condoms cannot be used simultaneously
- Diaphragm with spermicide
- Cervical cap with spermicide
- Vaginal Sponge with spermicide
- Progestogen-only oral hormonal contraception, where inhibition of ovulation is not the primary mechanism of action

[figure not shown]
Unacceptable Methods of Contraception

[figure not shown]
- Periodic abstinence (calendar, symptothermal, postovulation methods)
- Withdrawal (coitus interruptus)
- Spermicide only
- Lactation amenorrhea method

[figure not shown]
Collection of Pregnancy Information

[figure not shown]
Guidance for collection of Pregnancy Information and outcome of pregnancy on the Pregnancy Surveillance Form is provided in Section 8.6.2.1.5 and the Appendix for AEs and SAEs Definitions and Procedures for Evaluating, Follow-up, and Reporting (Appendix 2).

[figure not shown]

[figure not shown]

[figure not shown]

[figure not shown]

APPENDIX 7 CHILD-PUGH SCORING

Parameter	Classification	Score
Bilirubin (Total)	< 2 mg/dL (< 34.2 μmol/L)	+1
	2-3 mg/dL (34.2-51.3 μmol/L)	+2
	> 3 mg/dL (> 51.3 μmol/L)	+3
Albumin	> 3.5 g/dL (> 35 g/L)	+1
	2.8-3.5 g/dL (28-35 g/L)	+2
	< 2.8 g/dL (< 28 g/L)	+3
International Normalized Ratio	< 1.7	+1
	1.7-2.2	+2
	> 2.2	+3
Ascites	Absent	+1
	Slight	+2
	Moderate	+3
Encephalopathy	No encephalopathy	+1
	Grade 1-2	+2
	Grade 3-4	+3

APPENDIX 8 FORMULAE FOR MEASUREMENTS

• MELD Score = (9.57*ln[creatinine]) + (3.78 * ln[Bilirubin]) + (11.20* ln[INR]) + 6.43

Method of BMI Calculation:

- Use actual height and weight collected on the same day. Whenever possible, body weight should be measured using the same scale throughout the study.
- To calculate BMI:
 - \circ Convert weight pounds to kg (kg = pounds / 2.2)
 - \circ Convert height inches to centimeters (cm = inches \times 2.54)
 - o BMI = (weight in kg) / (height in cm/100)²
 - o Round to 1 decimal place (if 0.05 or greater, round up)

2.0 Study Objectives

2.1 Primary Study Objectives

Part 1: To assess the effect of treatment with 90 mg once every week (QW) of BMS-986263 on the proportion participants with ≥ 1 stage improvement in liver fibrosis (METAVIR score), as compared to placebo after 12 weeks of treatment.

2.2 Secondary Study Objectives

Part 1:

- To assess the effect of treatment with 90 mg QW BMS-986263 on the change in collagen proportionate area (CPA), as compared to placebo after 12 weeks of treatment
- To assess the effect of treatment with 90 mg QW BMS-986263 on the proportion of participants with ≥ 1 stage improvement in liver fibrosis (Ishak score), as compared to placebo after 12 weeks of treatment
- To assess the effect of treatment with 90 mg QW BMS-986263 on the proportion of participants with ≥ 2 stage improvement in liver fibrosis (METAVIR score), as compared to placebo after 12 weeks of treatment
- To assess the effect of treatment with 90 mg QW BMS-986263 on the proportion of participants with ≥ 2 stage improvement in liver fibrosis (Ishak score), as compared to placebo after 12 weeks of treatment

Statistical Analysis Plan Version Date: 19-Feb-2019

- To assess the effect of treatment with 90 mg QW BMS-986263 on the proportion of participants with a ≥ 15% reduction in liver stiffness as measured by magnetic resonance elastography (MRE) compared to placebo at Week 12
- To assess the effect of treatment with 90 mg QW BMS-986263 on the change in liver stiffness from baseline as measured by MRE compared to placebo at Week 12
- To assess the safety and tolerability of 45 mg QW and 90 mg QW BMS-986263 throughout 36 weeks of treatment and follow-up
- To assess the pharmacokinetics (PK) of 45 mg QW and 90 mg QW BMS-986263
- To describe the effect of treatment with 45 mg QW BMS-986263 on liver fibrosis after 12 weeks of treatment

3.0 Study Design

3.1 Overall Study Design

This is a randomized, double-blind, placebo-controlled, parallel group study to evaluate the efficacy and safety of BMS-986263 in adults with advanced hepatic fibrosis due to HCV who have achieved sustained virologic response (SVR) for at least 1 year. This study will enroll approximately 60 participants in Part 1, randomized in a 1:2:1 ratio to receive 45 mg BMS-986263 QW, 90 mg BMS-986263 QW, or placebo QW for 12 weeks. The primary study endpoint is the proportion of participants who achieve ≥ 1 stage improvement in liver fibrosis (METAVIR score) on biopsy after 12 weeks of treatment in Part 1.

Page 6 of 30

Part 1: The primary objective of Part 1 is to assess the effect of treatment with 90 mg QW BMS-986263 on the proportion participants with ≥ 1 stage improvement in liver fibrosis (METAVIR score) on biopsy, as compared to placebo after 12 weeks of treatment. This part of the study includes:

- · A screening period
- A 12-week, double-blind treatment period, during which participants will receive 1 of the 3 following treatments: 45 mg BMS-986263 QW, 90 mg BMS-986263 QW, or placebo QW
- A 24-week follow-up period

A schematic of the study design is provided in Figure 1.

Figure 1 Study Design Schematic

PBO = placebo; QW = once weekly; Wk = Week

3.2 Sample Size Considerations

This study will enroll approximately 60 participants in Part 1, randomized via IRT (interactive response technology) in a 1:2:1 ratio to receive 45 mg BMS-986263 QW, 90 mg BMS-986263 QW, and placebo QW. The sample size for Part 1 is not based on formal statistical justification. Part 1 of the study is designed for estimation purposes; no statistical testing will be performed. A 95% confidence interval (CI) for the primary endpoint of proportion of participants with \geq 1 stage improvement in fibrosis on biopsy after 12 weeks of treatment and odds-ratios between treatment groups will be utilized for this purpose.

3.3 Randomization

[figure not shown]
Approximately 60 participants meeting eligibility criteria during the screening period for Part 1 will be randomized into the Part 1 treatment period. These participants will be randomized via IRT in a 1:2:1 ratio to 45 mg BMS-986263 QW, 90 mg BMS-986263 QW, or placebo QW in a double-blind manner. The randomization of participants will be stratified by fibrosis stage as assessed by local pathologist (METAVIR Stage 3 or Stage 4).

4.0 Study Variables and Covariates

4.1 Primary Efficacy Variable

The primary efficacy variable is the METAVIR fibrosis score, which will be determined by a central pathologist using liver biopsies.

Page 7 of 30

Statistical Analysis Plan Version Date: 19-Feb-2019

The METAVIR system is used to assess the extent of inflammation and fibrosis by histopathological evaluation in a liver biopsy of patients with HCV. It assesses liver biopsies for activity grade (A0-A3: A0 = no activity, A1 = mild activity, A2 = moderate activity, A3 = severe activity) and fibrosis stage (Stage 1 - 4: 1 = portal fibrosis without septa; 2 = portal fibrosis with few septa; 3 = numerous septa without cirrhosis; or 4 = cirrhosis).

The METAVIR fibrosis score will also be used as a secondary efficacy variable for some endpoints.

4.2 Secondary Efficacy Variables

4.2.1 Collagen Proportionate Area

There can be considerable intra- and inter-individual variation in the assessment of liver biopsy to determine fibrosis stage. Assessment of CPA is a method by which the amount (percentage) of collagen in stained tissue sections is analyzed using morphometric image analysis. This technique allows for a quantitative assessment of fibrosis. This morphometric assessment will be performed by a blinded central pathologist. The percentage of collagen proportionate area will be provided.

4.2.2 Ishak Liver Fibrosis Score

Ishak liver fibrosis scores will be done by the central pathologist using the liver biopsies. The Ishak system (0 through 6 scale) was developed to grade portal-based liver fibrosis associated with viral hepatitis:

[figure not shown]
- 0: No fibrosis
- 1: Fibrous expansion of some portal areas, with or without short fibrous septa
- 2: Fibrous expansion of most portal areas, with or without short fibrous septa
- 3: Fibrous expansion of most portal areas with occasional portal to portal bridging
- 4: Fibrous expansion of portal areas with marked bridging (portal to portal as well as portal to central)
- 5: Marked bridging (portal-portal and/or portal-central) with occasional nodules (incomplete cirrhosis)
- 6: Cirrhosis, probable or definite

4.2.3 Liver Stiffness by MRE

MRE is a noninvasive medical imaging technique approved by FDA in 2009. It quantitatively measures in kilopascal (kPA) the stiffness of soft tissues by introducing shear waves and imaging their propagation using magnetic resonance imaging (MRI). In this study, MRE will be used to quantitate liver stiffness as a surrogate biomarker of liver fibrosis. The central imaging facility will perform all MRE imaging analyses.

[figure not shown]

Page 8 of 30

[figure not shown]
Protocol no: IM025006

Statistical Analysis Plan Version Date: 19-Feb-2019

[figure not shown]
Page 9 of 30

Statistical Analysis Plan Version Date: 19-Feb-2019

4.5 Safety Variables

The safety of BMS-986263 will be asset	essed by evaluation of the incidence of a	l adverse events (AEs) and
serious adverse events (SAEs),		electrocardiogram (ECG)
monitoring, physical examinations, vit	al signs,	

4.5.1 Adverse Events

The definition of adverse events and serious adverse events as well as their time periods for collection can be found in the protocol Section 8.6.2 and Protocol Appendix 2. The event (term), along with its start and stop dates, maximum intensity (mild, moderate, or severe), seriousness (yes/no), relationship to the IP (yes/no), action taken with regard to the IP, and outcome will be recorded in the electronic case report form (eCRF).

Additional details for infusion related reactions will be collected including clinical signs and symptoms as well as the location, characteristics and severity of those signs or symptoms, and start and end time of the reaction.

4.5.2 Laboratory Data

Hematology, serum chemistry, urinalysis, and other assessments are listed below. A central laboratory will perform the analyses and will provide reference ranges for these tests.

Hematology		
CBC PT PTT INR	WBC (absolute)HemoglobinHematocritMCV	 MCH concentration Red cell distribution width Platelet count
Blood Chemistry		
 AST ALT Total bilirubin Direct bilirubin ALP LDH GGT Creatinine 	 Creatinine clearance Creatine kinase BUN Uric acid Glucose PTH Total protein Albumin sodium 	 Potassium Chloride Carbon dioxide Calcium Phosphorus Glomerular filtration rate
Urinalysis		
pHSpecific gravityProtein	GlucoseKetonesLeukocyte esterase	 Nitrite Creatinine Microscopic examination (only to follow-up abnormal findings)
HbA1C		
Serology/viral load	HCV viral load (RNA)HBsAg	HbcAb and HBV viral DNA if HbcAb-positive.

Sponsor: Bristol-Myers Squibb Statistical Analysis Plan
Protocol no: IM025006 Version Date: 19-Feb-2019

Other Analyses		
•	FSH	Illegal drugs of abuse (urine or serum;
•	AFP	amphetamine, barbiturate, benzodiazepines,
		marijuana, cocaine, opiate, or PCP)
_		 pregnancy test (WOCBP only).
AFP = alpha-fetoprotein; ALP = alkaline pho	osphatase:	ALT = alanine aminotransferase.
AST = aspartate aminotransferase;	op.nataco,	BUN = blood
urea nitrogen;		
CBC = complete blood count;		CVD = cardiovascular disease;
DNA = deoxyribonucleic acid;	TCLL - follo	GGT = gamma-glutamyl transferase;
HBsAg = hepatitis B surface antigen; HbcAl		cle stimulating hormone; HbA1c = hemoglobin A1c;
INR = international normalized r		
corpuscular hemoglobin; MCV = mean corp		
		PT = prothrombin time; PTH = parathyroid hormone;
PTT = partial thromboplastin time;	WBC = white blo	ood cell; WOCBP = women of childbearing potential

4.5.3 Electrocardiograms

Variables collected from a central vendor for electrocardiograms include mean heart rate, RR interval, PR interval, QRS duration, QT interval, QTcB interval, QTcF interval, interpretation, atrioventricular conduction, axis and voltage, chamber hypertrophy or enlargement, intraventricular-intra atrial conduction, myocardial infarction (if applicable), pacemaker status, sinus node rhythms and arrhythmias (if applicable), supraventricular arrhythmias and tachyarrhythmias, ST segment, T and U waves, technical quality, and ventricular arrhythmias and tachyarrhythmias.

4.5.4 Physical Examinations

A full examination will include general appearance, skin, head, eyes, ears, nose, throat, neck, thyroid, chest/lungs, heart, abdomen, lymph nodes, extremities, height, and body weight. Abbreviated physical examinations will be performed at the other time points, which will include an abdominal exam, assessments for ascites and hepatic encephalopathy, as well as symptom-focused assessments. An abbreviated examination may note any changes in the participant's condition (body systems) since the last assessment and does not preclude examination of any of the other body systems as clinically indicated. Physical exam variables include exam date and time body system, result, whether abnormal and if abnormal the result, and whether this is clinically significant.

Page 12 of 30

Statistical Analysis Plan Version Date: 19-Feb-2019

4.5.5 Vital Signs

Vital signs variables include height, weight, body mass index (BMI), temperature, systolic blood pressure, diastolic blood pressure, heart rate, respiratory rate, and clinical significance.

4.5.6 Bone Density Testing

DXA will be performed to assess bone density. The clinical sites will be trained in imaging procedures prior to scanning the first study participant. The baseline Z-score to determine participant's eligibility will be based on local radiologist read at the clinical site.

Variables include the date and time of assessment, and total BMD and T- and Z-scores for hip, lumbar spine, and femoral neck. In addition, the number of lumbar spine segments and the segments included in the assessment (L1, L2, L3, L4) will be collected.

4.6 Other Variables

Other variables that will be collected include participant demographics (birth date, age, sex, ethnicity, race), general medical history, prior and concomitant medications, hospitalizations, and diagnostic and/or medical procedures that occur.

In addition, variables will be collected for informed consent and re-consent if applicable, eligibility including pregnancy testing and childbearing potential, randomization or reason for non-randomization, ultrasound for detection of hepatocellular carcinoma (HCC) at screening, and previous enrollment and dates enrolled in a previous BMS study. Details of the regimen used to treat and cure Hepatitis C (date of sustained virologic response, treatment, start and end date, dose and unit per administration, frequency, and route) as well as disease diagnosis and specific disease history (date of diagnosis, and history of impaired fasting glucose and diabetes) will also be recorded.

Treatment exposure variables will include start and end dates and times, total volume prepared (mL), actual volume and whether different from total volume prepared and reason (Adverse Event or Other), infusion rate (mL/hour), whether administration was interrupted and reason (Adverse Event or Other), and whether administration was resumed. Pre-treatment antihistamine and corticosteroid variables will include the medication name, date and start and end times, dose and unit, and route.

End of treatment and end of study dates and reasons will be collected. When applicable, date of death, primary cause of death, and whether autopsy was performed will be recorded.

4.7 Pharmacokinetics	Variables	
•	at several time points according to the samp from participants randomized to placebo will n	•

Page 13 of 30

Statistical Analysis Plan Version Date: 19-Feb-2019

4.9 Predetermined Covariates and Prognostic Factors

Subgroup analyses will be presented by baseline METAVIR fibrosis stage determined by central pathologist where specified in the TFL shells. Other subgroups may include Pro-C3 level (split at the median). Summary tables and/or figures may be provided for these analyses.

5.0 **Definitions**

5.1 Screen Failures, Retesting, and Rescreening

Screen failures are defined as participants who consent to participate in the clinical study (i.e., enroll) but are not subsequently randomized into the study.

Rescreening is allowed but the participant must wait at least four weeks after the date of screen failure to attempt to re-enroll. The protocol delineates which screening procedures need repeating and under what circumstances.

5.2 Baseline

Baseline is defined as the last measurement prior to first dose of double-blind study treatment (BMS-986263 or matching Placebo). Admissible prior biopsies and biopsies performed during screening will be used to determine eligibility (i.e., liver fibrosis stage), and tissue from these biopsies will be used as the baseline sample for the primary endpoint analysis. The requirement that prior biopsies occur within 8 weeks prior to screening ensures that the acquired biopsy sample accurately reflects the condition of the participant at baseline to enable a valid analysis.

Page 14 of 30

Many pre-infusion measures are collected per-protocol on study day 1 (randomization). For variables specified in the schedule of events to be collected prior to infusion the analysis will assume they were collected per-protocol and as such they will qualify as baseline measures.

5.3 Actual Treatment

All analyses conducted on the Safety Analysis Set will be performed using the Actual Treatment. Actual treatment is defined as the highest dose and frequency of active study treatment (BMS-986263) that a participant receives at any time during their participation in the study. Participants who only receive Placebo will be analyzed as such.

5.4 Change and Percentage from Baseline

Change from baseline (CFB) will be calculated as (post-baseline value – baseline value). CFB will be calculated for participants with both a baseline and post-baseline value as applicable. Percent CFB will be calculated as (CFB/baseline)*100, where applicable. If a baseline value has not been recorded for a parameter, then CFB will not be calculated for that parameter. Participants with missing CFB values will be excluded from analyses in which CFB is the endpoint. In cases where baseline is zero and the post-baseline value is also zero percent CFB will be considered zero percent.

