8.1.2 Part 1 Treatment Period and Follow-up

Approximately 60 participants meeting eligibility criteria during the screening period will be randomized into the Part 1 treatment period. These participants will be randomized via interactive response technology (IRT) in a 1:2:1 ratio to receive 45 mg BMS-986263 QW, 90 mg BMS-986263 QW, or placebo QW in a double-blind manner. The randomization of participants will be stratified by fibrosis stage (METAVIR Stage 3 or Stage 4). Participants will receive study treatment via IV administration for a total of 12 weeks.

Fibrosis stage will be assessed by liver biopsy during the screening period and on Day 85. Liver stiffness will be assessed by MRE at baseline, Day 43, Day 85 (primary efficacy endpoint), Day 169, and Day 253.

After 12 weeks (Day 85) of treatment, participants in Part 1 will enter the 24-week off-treatment follow-up period. During this time, they will not receive infusions of either active drug or placebo.

See the Schedule of Activities for Part 1 in Table 2 and Table 3 (Section 1.2).

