9.5 Efficacy Analyses

All efficacy analyses, both primary and secondary, will be performed on the Modified-Intent-to-Treat (mITT) analysis set.

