9.5.2.1 Collagen Proportionate Area

The change from baseline in collagen proportionate area will be analyzed using an Analysis of Covariance (ANCOVA) at Week 12 for Part 1. The model will include a fixed factor for treatment group and a covariate for baseline CPA. Contrasts will be used to compare the adjusted mean change from baseline between each treatment group and placebo and CIs will be presented for each comparison. In addition to actual, change from baseline, and percent change from baseline summaries by time point, box plots by treatment group and spaghetti plots by participant by treatment group will be provided.

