9.5.2.3 MRE Liver Stiffness

[figure not shown]
An analysis similar to that used for the primary efficacy variable will be conducted for the proportion of participants with ≥15% decrease in MRE liver stiffness. An analysis similar to that used for the secondary endpoint of CPA will be conducted for continuous MRE liver stiffness.

Page 22 of 30

[figure not shown]

Protocol no: IM025006

Statistical Analysis Plan Version Date: 19-Feb-2019

Page 23 of 30

Protocol no: IM025006

Statistical Analysis Plan Version Date: 19-Feb-2019

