9.7 Methods for Handling Dropouts and Missing Data

Imputation for missing dates for AEs and concomitant medications have been addressed in previous sections (5.6 and 5.12 respectively).

Assumptions for laboratory values below or above the limits of quantification have been specified in Section 9.6.5. Participants without an efficacy measurement at Week 12 will be considered as "non-responders". No other imputations or missing data analyses are planned.

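### The Day 85 MRE stiffness analysis drops participants without a Day 85 scan and ignores their Day 43 scan; a repeated-measures model would reduce, though not always remove, the resulting dropout bias

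*SAP*

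**What the plan says.** - **Model.** SAP 9.5.2.3 states "An analysis similar to that used for the secondary endpoint of CPA will be conducted for continuous MRE liver stiffness". The CPA analysis in SAP 9.5.2.1 is made "using an Analysis of Covariance (ANCOVA) at Week 12 for Part 1", and "The model will include a fixed factor for treatment group and a covariate for baseline CPA". For MRE this means one visit, with treatment and baseline MRE as the only terms.
- **Missing values.** SAP 5.4: "Participants with missing CFB values will be excluded from analyses in which CFB is the endpoint". SAP 9.7 counts participants without a Week 12 efficacy measurement as non-responders, which can apply only to the binary endpoints, and then adds "No other imputations or missing data analyses are planned".
- **Population.** SAP 9.5: "All efficacy analyses, both primary and secondary, will be performed on the" mITT set, that is, everyone randomized who received at least one dose (SAP 6.0).
- **Schedule.** Protocol 8.1.2: "Liver stiffness will be assessed by MRE at baseline, Day 43, Day 85", with two later scans in follow-up. Protocol Table 2 shows the Day 43 and Day 85 scans within the treatment period.
- **After stopping.** Participants who stop treatment stay in follow-up (Protocol 8.4.6.1). An early-termination MRE is required only when the last MRE is more than 4 weeks old (Protocol 8.6.1.2).

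**The concern.** The continuous MRE analysis is labelled mITT but in effect uses only participants with an observed Day 85 scan. A participant with a Day 43 scan and no Day 85 scan contributes nothing, although the Day 43 value says something about the missing one. The same person is kept in the companion endpoint (at least 15% reduction in stiffness) as a non-responder. One measurement is thus handled in two ways, and the SAP does not say why.

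Part 1 is for estimation, so the point estimate and its interval are the product. The ANCOVA is unbiased if missingness depends only on treatment and baseline. If participants on 90 mg whose stiffness looks poor at Day 43 are less likely to have a Day 85 scan, those who remain look better than the arm as a whole, and the effect on stiffness is overstated.

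**Working it through.** **No plan figure to reproduce.** The documents give no power or precision figure for MRE or for Part 1. Their only power figure, 80% for the Part 2 trend test, reproduces (80.2% by formula) but does not bear on this point.

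**Inputs from the documents.** About 60 participants at 1:2:1 give 15 on 45 mg, 30 on 90 mg and 15 on placebo. The comparison of 90 mg with placebo therefore has 45 participants.

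**Assumptions, not in the documents.** Day 85 scans missing: 10% or 20% (the protocol's 10% in 9.1 is for Part 2 and for stopping treatment). Residual SD of change: 1. Residual correlation ρ between Day 43 and Day 85: 0.5 to 0.9. Placebo missingness is random; 90 mg missingness is selective.

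**1. Who is affected.** At most 0.10 × 45 = 4.5 or 0.20 × 45 = 9 participants have a Day 43 but no Day 85 scan. The early-termination rule helps to create this group: anyone leaving up to about Day 43 + 28 = Day 71 needs no further scan.

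**2. Complete data.** With treatment-by-visit and baseline-by-visit terms and unstructured covariance, both visits have the same regressors. The model's Day 85 contrast then equals the ANCOVA estimate. The two differ only when scans are missing.

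**3. Expected bias.** Let s be the shift, among 90 mg participants who keep a Day 85 scan, in the mean of whichever value drives dropout.
- Dropout driven by Day 43: ANCOVA bias = ρs. The repeated-measures model subtracts ρ × s, leaving 0.
- Dropout driven by the Day 85 value itself: ANCOVA bias = s. The model subtracts ρ × ρs, leaving about (1 − ρ²)s.

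The simulated ANCOVA bias in the second case gives s = 0.127 (10% missing) and 0.231 (20%). At ρ = 0.7 the first case should then give 0.7 × 0.127 = 0.089 and 0.7 × 0.231 = 0.162. In the second case about 0.51 × 0.127 = 0.065 and 0.51 × 0.231 = 0.118 should remain.

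**4. Simulation** (6,000 trials per scenario, 30 vs 15, ρ = 0.7, simulation error about 0.005). Bias is in residual SD; negative favours 90 mg.

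| Dropout on 90 mg | 10% missing: ANCOVA → repeated measures | 20% missing: ANCOVA → repeated measures |
|---|---|---|
| Driven by Day 43, all have a Day 43 scan | −0.091 → −0.006 | −0.164 → −0.005 |
| Same, half leave before Day 43 | −0.091 → −0.046 | −0.164 → −0.076 |
| Driven by Day 85, all have a Day 43 scan | −0.127 → −0.070 | −0.231 → −0.127 |
| Same, half leave before Day 43 | −0.127 → −0.097 | −0.231 → −0.173 |

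These agree closely with step 3. The reductions in rows 2 to 4 are 49% and 54%, 45% and 45%, and 24% and 25% (for example 1 − 0.097/0.127 = 24%). At ρ = 0.9 the row 3 figures are −0.126 → −0.030 and −0.229 → −0.052. With completely random dropout neither method is biased.

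**5. Precision under random dropout.** With a fraction m missing and every leaver scanned at Day 43, the standard error ratio (repeated measures to ANCOVA) is about √(1 − mρ²). For m = 0.2 and ρ = 0.9 this is √(1 − 0.162) = 0.92; for m = 0.1 and ρ = 0.5 it is √(1 − 0.025) = 0.99. The simulated ratios are 0.95 to 0.98 at 10% and 0.91 to 0.97 at 20%.

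**6. Bias against sampling error.** The full-data standard error is about √(1/15 + 1/30) = 0.32 SD. In row 1 the ANCOVA bias is 0.091/0.338 = 0.27 and 0.164/0.355 = 0.46 of its simulated standard error.

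**The case against.** The strongest case against is that the bias is hypothetical and small. No treatment-stopping criterion in Protocol 8.4.6.1 refers to liver stiffness. If leaving is unrelated to stiffness given arm and baseline, the ANCOVA is unbiased. Follow-up after stopping treatment and the early-termination scan both limit missing data. Even the assumed bias is under half a standard error, on a secondary endpoint with no testing. Protocol 9.3.1.2 allows ANCOVA. Text after SAP 9.5.2.3 is not visible, and Protocol Table 4 points to a Week 6 MRE analysis in a section that is not visible either, so Day 43 may be analysed elsewhere.

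Most of this stands as a limit on importance. It does not answer the point: the visible text fixes the Day 85 analysis as a single-visit ANCOVA, and the alternative needs a weaker missingness assumption.

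A reader might infer more than the documents support:
- **That the new model removes dropout bias.** It does so only if missingness depends on treatment, baseline and the observed Day 43 MRE. It recovers nobody who leaves before Day 43. The near-zero results in row 1 come from a scenario in which that condition holds by construction.
- **That only treatment completers are analysed.** Participants who stop treatment remain in follow-up and can have a Day 85 scan.
- **That the SAP breaks its mITT commitment.** It names the set and openly states the exclusion. The effective sample is smaller than the label suggests, but this is disclosed.
- **That the change is free.** The model has 3 × 2 + 2 = 8 mean and 3 covariance parameters. It predicts leavers' Day 85 values from similar participants who stayed, so the treatment of discontinuation has to be stated.

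**Conclusion.** The point holds as a modest, inexpensive improvement. The planned Day 85 MRE analysis excludes participants without a Day 85 scan and makes no use of a Day 43 scan that the trial collects. A two-visit repeated-measures model loses nothing when data are complete and had less bias in every selective-dropout scenario examined.

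At ρ = 0.7 and 10% to 20% missing scans, bias falls from about 0.09–0.16 SD to near zero in the favourable case, and by roughly a quarter to a half in the less favourable ones. Under random dropout the standard error is about 2% to 9% smaller across correlations of 0.5 to 0.9. All of these sizes rest on assumed missingness, correlation and dropout mechanism. The documents show that bias is possible, not that it is present.

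**What to change.** For continuous MRE, amend SAP 9.5.2.3, and SAP 5.4 and 9.7 to match, before unblinding:

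1. Replace the Week 12 ANCOVA with a repeated-measures model on change at Day 43 and Day 85. Terms: treatment, visit, treatment-by-visit, baseline MRE and baseline-by-visit, with unstructured covariance. The Day 85 contrast of each dose with placebo is the endpoint.
2. State the missing-at-random assumption.
3. State how early-termination scans are assigned to visits, and whether scans after treatment discontinuation are used.
4. Add a delta-adjusted sensitivity analysis. Worsening the implied Day 85 values of 90 mg participants without a scan by δ moves that arm's mean by (fraction missing) × δ, so a short table over δ is enough.
5. Keep ANCOVA for CPA, which has a single scheduled post-baseline value.

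The cost is SAP wording and slightly more programming. No extra scans are needed. Protocol 9.3.1.2 says only that ANCOVA may be used and leaves missing data to the SAP, so a SAP change appears sufficient.
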